4.5. Handling of Dropouts or Missing Data

No adjustments for missing data and no imputation methods are planned for this study.

4.6. Treatment Group Comparability

4.6.1. *Patient Disposition*

Subject disposition information will be summarized for all subjects. Summaries will include: the number of subjects in each analysis population, the number of subjects completed the study, and the number of subjects discontinued study and its reason. All subjects randomized in the study will be included in the summary table. Patient allocation by investigator or site will be summarized. Patient allocation by investigator or site will also be listed as well.

4.6.2. *Protocol Deviations*

Listings of subjects with significant protocol deviations or violations will be provided. The following list of significant protocol violations will be determined from the clinical database and from the study clinical/medical group:

- Lack of informed consent or late informed consent
- Violations of inclusion/exclusion criteria
- Significant violations of prohibited concomitant medication usage as determined by the clinical/medical group
- Other significant protocol violations as determined by the clinical/medical group

4.6.3. *Patient Characteristics*

The following patient characteristics at baseline will be summarized by treatment group for all ITT patients:

- Demographic (age, gender, ethnic origin, height, weight, BMI)
- Medical history and Pre-existing condition

Medical history and pre-existing conditions will be summarized by preferred term (PT) within system organ class (SOC). Medical history is defined as illness(es) that ended prior to the signing of informed consent. Pre-existing conditions and AEs at baseline are those AEs occurring during the baseline/screening visits that is Visit 1, 2 and 3.

4.6.4. *Prior and Concomitant Therapy*

Verbatim terms on eCRFs will be mapped to Anatomical Therapeutic Chemical (ATC) class and Generic Drug Names using the World Health Organization (WHO) Drug Dictionary Enhanced (WHODDE) B2 format, March 1, 2015 release.

Prior medications are defined as medications started to take prior to the first injection. Concomitant medications are defined as medications started on or after the day of first injection of the study drug during the study.

Prior and concomitant medications will be tabulated for the ITT population by WHODDE ATC level 2 classifications, preferred term, and treatment. If a subject reports the same preferred term multiple times, then the frequency of that preferred term will only be incremented by one. As with the preferred term, if a subject reports multiple medications within the same ATC level 2 classification, then the frequency of that ATC level 2 classification will only be incremented by one. Percentages will be calculated using the total number of subjects in the safety population. Each summary will be ordered by descending order of incidence of preferred term within each ATC class. Prior and concomitant medications will be included in a data listing.

4.6.5. *Treatment Compliance*

Not applicable.

4.7. *Efficacy Analyses*

The primary efficacy hypothesis test will be performed using a 5% significance level. For the secondary efficacy endpoints, hypothesis tests will be performed individually at the 5% significance level. All hypothesis tests will be performed with two-sided alternative hypotheses. No adjustments on the significance level for multiple comparisons are planned, as this is a phase 1/2 study. All efficacy analyses will be based on the ITT population.

4.7.1. *Primary Efficacy Analysis*

The primary objective of this study is to test the hypothesis that AstroStem is superior to placebo in the improvement on neurological/neurocognitive assessment from baseline to week 30 in patients with Alzheimer's Disease.

The primary analysis will evaluate the efficacy of AstroStem compared with placebo on the overall mean change from baseline to week 30 in ADAS-Cog score. The primary efficacy variable will be summarized with means, standard deviations, medians and ranges, overall and by group. The change from Baseline ADAS-Cog score will be analyzed with Student's t-test or Kruskal-Wallis test depending on the violation of normality assumption.

4.7.2. *Secondary Efficacy Analyses*

The secondary efficacy analyses will be summarized with means, standard deviations, medians and ranges for continuous variables including the changes from baseline at Week 30 in MMSE, CDR-SOB, NPI, GDS and ADCS-ADL.

These changes score from baseline at week 30 will be analyzed with Student's t-test or Kruskal-Wallis test depending on the violation of normality assumption. .

4.7.3. *Exploratory Efficacy Analyses*

Change from baseline scores at Visits 6, 9, 12 and 14 or Early Termination for: ADAS-Cog, MMSE, CDR-SOB, NPI, GDS, and ADCS-ADL will be summarized with means, standard deviations, medians and ranges by treatment group and visit. These changes score from baseline at Visits 6, 9, 12 and 14 or Early Termination will be analyzed with Student's t-test or Kruskal-Wallis test depending on the violation of normality assumption.

Biomarkers in blood [Amyloid beta 40, Amyloid beta 42, Amyloid precursor protein intracellular domain (AICD), soluble neuregulin-1 (sNRG-1)] will be summarized with means, standard deviations, medians and ranges for continuous variables and with counts and percentages for categorical variables. at baseline, Visit 13 and 14 or Early Termination

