4.1.2 Visit 2 (Week -4)

Visit 2 will occur approximately 4 weeks (\pm 1 week) after Visit 1. During this visit, the following assessments/procedures should be performed:

- Confirm eligibility and perform randomization instructed in Section 3.5.6.
- Measure vital signs (sitting blood pressure, pulse, breathing, and temperature) and weight.
- Record any changes in concomitant medications.
- Record any adverse events, if applicable.
- In sterile conditions, collect blood and harvest approximately 30 mL of fat using the syringe liposuction technique with Tumescent (or super-wet) local anesthesia (Please see the detail procedures in Appendix 9).
- Ship the packaging box containing the harvested syringes and serum tubes to the lab designated by the sponsor (pre-labeled).

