3.1. Summary of Study Design

This is a randomized, double-blind, placebo-controlled study to evaluate the efficacy and safety of AstroStem for the treatment of Alzheimer's Disease. Three investigational centers in the United States may be utilized so that a total of approximately 22 subjects will be randomized. At Week -4, 30 mL of abdominal adipose tissue will be taken by liposuction from subjects. The adipose tissue samples will be sent to Biostar Stem Cell Research Institute to isolate AdMSCs. The isolated AdMSCs or saline will be sent to the clinical sites with identical syringes to preserve double-blinding of the study. A total 2×10^8 AdMSCs in 220 mL of saline or the same volume of saline will be administered via I.V. at Week 0. This procedure will be repeated 9 times at 2-week interval. Subjects will be scheduled for two follow-up visits at Weeks 30 and 52 to evaluate primary and secondary outcome endpoints. The schedule of Assessments is illustrated in [Table 4](#).

Table 4. Schedule of Assessments

Procedure	Screen		Treatment											Follow-up		Early Termination
	V1	V2	V3	V4	V5	V6	V7	V8	V9	V10	V11	V12	V13	V14		
Tested Group	-W8	-W4	W0	W2	W4	W6	W8	W10	W12	W14	W16	W18	W30	W52		
Informed Consent ¹	V															
Inclusion/Exclusion Criteria	V															
Demographic information	V															
Medical/medication history	V															
Physical examination	V		V		V			V			V	V	V	V		
Vital signs	V	V	V	V	V	V	V	V	V	V	V	V	V	V		
Hematology, serum chemistry, and urinalysis ²	V		V		V			V			V	V	V	V		
Pregnancy test ³	V		V								V	V	V	V		
Electrocardiogram	V		V		V			V			V	V	V	V		
Chest X-ray	V															
Liposuction		V														
Serum for IP		V	V		V		V		V							
ADAS-Cog			V		V			V			V	V	V	V		
MMSE	V		V		V			V			V	V	V	V		
CDR-SOB			V		V			V			V	V	V	V		
NPI			V		V			V			V	V	V	V		
GDS			V		V			V			V	V	V	V		
C-SSRS			V		V			V			V	V	V	V		
ADCS-ADL			V		V			V			V	V	V	V		
MRI Scan	V							V				V	V	V		

Biomarker ⁴			V									V	V	V
Drug administration			V	V	V	V	V	V	V	V	V			
Concomitant medications		V	V	V	V	V	V	V	V	V	V	V	V	V
Adverse events		V	V	V	V	V	V	V	V	V	V	V	V	V

¹ Informed Consent Form should be signed prior to any clinical trial related activities

² See Appendix 1 for the complete list of laboratory tests

³ Serum pregnancy test is performed for all females of childbearing potential.

⁴ Amyloid beta 40, Amyloid beta 42, Amyloid precursor protein intracellular domain (AICD), soluble neuregulin-1 (sNRG-1)

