4.3. Analysis Populations

4.3.1. *Intent-to-Treat Population*

An intent-to-treat (ITT) population will include subjects who received at least one intravenous injection and have post-injection efficacy measurements. This population will be evaluated for all efficacy variables.

4.3.2. *Per-Protocol Population*

All subjects valid for ITT who complete Visit 13 (Week 30) will be 'valid per protocol' (also called 'valid for efficacy'). Additional criteria may be added prior to unblinding the study database. As with the ITT population, this per-protocol (PP) cohort will also be evaluated for all efficacy variables.

4.3.3. *Safety Population*

A safety population will include subjects who received at least one intravenous injection and have post-injection safety measurements. This population will be evaluated for all safety variables.

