4.4. Baseline and Postbaseline Definition

Table 5 describes the rules for determining the patient population and baseline and postbaseline observations for study and type of analysis.

Table 5. Patient Population with Baseline and Postbaseline Definitions by Type of Analysis

Study Period/Analysis	Patient Population	Baseline Observation	Postbaseline Observation(s)
Treatment Period			
Primary Efficacy analyses	ITT Population with a baseline and at least 1 postbaseline observation	Visit 3	Visit 13
TEAEs	Safety Population	All Visits 1-3	All Visits 3.01-14
Serious Adverse Events, Discontinuations due to Adverse Events	Safety Population	N/A	
C-SSRS analyses	Patients with a baseline and at least 1 postbaseline C-SSRS assessment	All Prior History: Visits 1-3 including	All Visits 3.01-14
Treatment-emergent abnormal laboratory values	Safety Population with normal laboratory values at all nonmissing baseline visits (with respect to direction being analyzed) and who have at least 1 postbaseline observation	Low: Minimum from Visits 1-3 High: Maximum from Visits 1-3 Abnormal: All Visits 1-3	Low: Minimum from Visits 3.01-14 High: Maximum from Visits 3.01-14 Abnormal: All Visits 3.01-14
Treatment-emergent immunogenicity	Safety Population	Visit 3	All Visits 3.01-14
Treatment-emergent changes in temperature and weight	Safety Population with a baseline and at least 1 postbaseline observation	Low: Minimum from Visits 1-3 High: Maximum from Visits 1-3	Low: Minimum from Visits 3.01-14 High: Maximum from Visits 3.01-14
Treatment-emergent changes in blood pressures, pulse, and ECGs	Safety Population with a baseline and at least 1 postbaseline observation	Low: Last nonmissing from Visits 1-3 High: Last nonmissing from Visits 1-3	Low: Minimum from Visits 3.01-14 High: Maximum from Visits 3.01-14
Continuous safety analyses	Safety Population with a baseline and at least 1 postbaseline observation	Last of Visits 1-3	All scheduled visits 3 < Visits ≤ 14

ECGs = electrocardiograms; eCRF = electronic case report form; ITT = intent-to-treat; N/A = not applicable; TEAEs = treatment-emergent adverse events

Note: Visit 3.01 indicates the first unscheduled visit occurring after Visit 3 and prior to Visit 4.

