4.8. Safety Analyses

The safety and tolerability of treatment will be assessed by summarizing the following:

- AEs
- Treatment-emergent adverse events (TEAEs)
 - By PT
 - By SOC
 - By maximum severity
 - By considered to be related to investigational produce by investigator
- Serious Adverse Events (SAEs)
- AE leading to discontinuation
- Suicide-Related Thoughts and Behaviors
- Vital signs and weight
- Laboratory measurements
- Electrocardiograms (ECGs)

All safety analyses will be based on the safety population. AE rates will be summarized by treatment group and overall, and will be broken down by severity, seriousness and relation to study drug. Change of MRI, C-SSRS, physical examinations, vital signs, ECG

and standard laboratory results will be summarized with means, standard deviations, medians and ranges for continuous variables and with counts and percentages for categorical variables. Statistical tests are not planned for safety.

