4.8.1. Adverse Events

An AE is defined as any untoward medical occurrence in a subject who is administered a medicinal product and that does not necessarily have a causal relationship to the treatment. All AEs will be included in the data listings. Verbatim terms on case report forms will be mapped to preferred terms and system organ classes (SOC) using the Medical Dictionary for Regulatory Activities (MedDRA) (version 19.1).

A Treatment Emergent Adverse Event (TEAE) is defined as an adverse event that occurs on or after the treatment dose. TEAE summary will be displayed by treatment. Unless otherwise specified, summaries that are displayed by SOC and preferred terms will be ordered alphabetically by SOC, and within each SOC, preferred terms will also be ordered alphabetically. Summaries of the following types will be presented:

- Subject incidence of TEAEs by MedDRA SOC and preferred term.
- Subject incidence of TEAEs by MedDRA SOC, preferred term, and severity. Severity will be recorded as deemed by investigator. At each level of subject summarization, a subject is classified according to the highest severity if the subject reported one or more events.
- Subject incidence of study drug related TEAEs by MedDRA SOC and preferred term.
- Subject incidence of TEAEs by descending incidence of preferred terms.
- Subject incidence of serious TEAEs by MedDRA SOC and preferred term, if applicable.
- Subject incidence of TEAE leading to early termination by MedDRA SOC and preferred term, if applicable.

For each subject and for each adverse event, the duration of the event will be calculated as:

$$\text{Duration of AE} = \text{AE stop date} - \text{AE start date} + 1$$

The duration of AEs will be displayed in the data listing.

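### Adverse events between liposuction and the first infusion are classed as baseline and fall outside every TEAE table, and for never-infused subjects outside every Safety Population table

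*SAP*

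**What the plan says.** - **Procedure.** Protocol 4.1.2 has sites confirm eligibility, randomize, and then "harvest approximately 30 mL of fat using the syringe liposuction technique with Tumescent (or super-wet) local anesthesia". SAP 3.1 repeats it: "At Week -4, 30 mL of abdominal adipose tissue will be taken by liposuction from subjects". Protocol Appendix 9 adds an incision with sutures, tumescent lidocaine and epinephrine, a 60 mL blood draw and an intramuscular antibiotic. It recommends that a physician trained in resuscitation be available.
- **Classification.** SAP 4.6.3, on patient characteristics in the ITT population: "Pre-existing conditions and AEs at baseline are those AEs occurring during the baseline/screening visits that is Visit 1, 2 and 3". Table 5 in SAP 4.4 likewise sets the TEAE baseline at Visits 1-3 and the post-baseline window at "All Visits 3.01-14".
- **TEAE definition.** SAP 4.8.1: "A Treatment Emergent Adverse Event (TEAE) is defined as an adverse event that occurs on or after the treatment dose".
- **Population.** SAP 4.3.3: "A safety population will include subjects who received at least one intravenous injection and have post-injection safety measurements". SAP 4.8: "All safety analyses will be based on the safety population". The ITT population in SAP 4.3.1 also requires an infusion.
- **Wider summaries.** SAP 4.8 lists AEs as an item separate from TEAEs and plans AE rates by group and overall, split by severity, seriousness and relation to study drug. The Table 5 row for SAEs and discontinuations due to AEs gives no onset window. SAP 4.8.1 puts all AEs in listings, and SAP 4.6.1 covers all randomized subjects in disposition.

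**The concern.** Liposuction is the most invasive step in the trial, and no subject can receive an autologous adipose product without it. The protocol anticipates procedural risk: exclusion criteria 18 and 19 concern liposuction problems and local anesthetic allergy. A hematoma, infection or anesthetic reaction in the four weeks before Visit 3 is nevertheless handled like medical history. No analysis set or table is counted from the liposuction date.

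Safety is a primary endpoint (protocol 3.6.1). A reader of the TEAE tables would take them as the safety record of the treatment, yet they cannot show harm from obtaining the cells. Subjects harmed badly enough to stop before infusion are the ones most completely removed from the safety tables.

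**Working it through.** The plan states no figure on this point, so the check is mainly of text, followed by an illustration of scale.

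**Step 1. Order of events.** Protocol 3.5.1 and 4.1.2 place randomization and liposuction at Visit 2 (Week -4). Protocol 4.2.1 places the first infusion at Visit 3 (Week 0). Events in between arise after randomization and after a protocol-mandated procedure.

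**Step 2. Where each event can be shown.**

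| Output | Subject later infused | Subject never infused |
|---|---|---|
| Itemised tables in SAP 4.8.1 (all TEAE-based, including serious events and early terminations) | Excluded | Excluded |
| General AE-rate and SAE summaries (SAP 4.8, Table 5) | Undefined | Excluded (not in Safety Population) |
| Pre-existing condition table (SAP 4.6.3) | Included, if in ITT | Excluded (not in ITT) |
| AE listings | Included | Included |
| Disposition | Only if withdrawn for it later | Reason shown if it led to withdrawal |

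**Step 3. Attribution.** Protocol 7.2.1 asks the investigator only whether the study drug may have caused the event, and SAP 4.8 splits AE rates by relation to study drug. Even if an infused subject's procedural event enters the AE-rate summary, nothing there identifies it as procedural.

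**Step 4. Visit 3.** SAP 4.6.3 and Table 5 treat Visit 3 as baseline, and Table 5 starts post-baseline at Visit 3.01, the first unscheduled visit after it. The first infusion is given at Visit 3, and SAP 4.8.1 counts an event that "is defined as an adverse event that occurs on or after the treatment dose". An event on the first infusion day, after the dose, is therefore baseline under one rule and treatment-emergent under the other.

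**Step 5. Data capture.** Protocol 3.6.3 collects AEs at all visits, and 4.1.2 and 4.2.1 record them at Visits 2 and 3. Protocol 7.2 makes the investigator responsible for AEs after the first dose, and 7.3 starts SAE reporting at the first administration. The protocol thus conflicts on whether pre-infusion events are systematically captured.

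**Step 6. Scale (illustration).** Inputs: n = 22 (SAP 3.2) and an assumed procedural AE rate, because the documents give none.

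- Calendar share of the window: 4 / (4 + 52) = 4/56 = 7.1%. This measures time, not risk.
- Chance of at least one procedural AE, 1 - (1 - p)^22: p = 1% gives 19.8%; 2% gives 35.9%; 5% gives 67.6%; 10% gives 90.2%; 20% gives 99.3%.
- If k subjects have a procedural AE and withdraw before infusion, and all others enter the Safety Population:
  - k = 1: rate 1/22 = 4.5%; Safety Population tables show 0 of 21 from these events.
  - k = 2: rate 2/22 = 9.1%; tables show 0 of 20.
  - k = 3: rate 3/22 = 13.6%; tables show 0 of 19.
- If the same k subjects are infused, the TEAE tables still show none of these events. The general AE summary shows either 0 or k of 22, depending on how the undefined rule is read.

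**The case against.** A reader might infer that liposuction harm appears in no safety table at all, or that a subject harmed before infusion vanishes from the report. The documents do not support either reading. SAP 4.8 separates AEs from TEAEs and plans AE rates without an onset limit; protocol 6.1.7 does the same. The Table 5 row for SAEs and discontinuations sets no window. For subjects later infused, nothing excludes their procedural events from those summaries. For a never-infused subject, listings and disposition remain, protocol 3.3 requires the withdrawal reason to be recorded, and protocol 4.4 records AEs at early termination. This part of the objection stands.

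Three further points have weight:

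- Starting TEAEs at first dose is ordinary practice and fits an objective framed around AstroStem.
- Both arms undergo liposuction, so the comparison between arms is not shown to be biased.
- Under protocol 7.1.1, a condition that worsens after drug administration can count as an AE, so some complications would re-enter.

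These points limit the concern but do not remove it. A risk common to both arms cannot appear in a comparison between them; only an absolute table can show it. A complication that resolves or stays stable before the infusion does not re-enter. An AE-rate summary of undefined scope, with relation to study drug only, does not tell a reader how often the procedure caused harm.

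**Conclusion.** The concern holds in a bounded form. Two statements are certain from the text: events between liposuction and first infusion are outside every TEAE table, and for subjects never infused they are outside every Safety Population table. For subjects later infused, inclusion in the general AE and SAE summaries is undefined rather than ruled out, and procedural harm would not be identifiable there.

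The loss is of absolute procedural risk in up to 22 subjects, not of the randomized comparison. The range of 1 to 3 events in 22 is an assumption for illustration, as are the per-subject rates of 1% to 20%. The conclusion about the tables rests on the definitions and does not depend on those rates. The SAP should be amended on this point.

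**What to change.** 1. **SAP 4.3:** add a procedure safety set of all subjects who had liposuction, infused or not.
2. **SAP 4.8.1:** add a table of AEs and SAEs with onset from the start of liposuction to the first infusion, by system organ class and preferred term, severity and seriousness, overall and by arm. Add relation to the procedure if an eCRF item is provided for it.
3. **SAP 4.6.3 and Table 5:** limit pre-existing conditions and baseline AEs to onset before liposuction. Classify Visit 3 events by onset relative to the infusion, so that these sections agree with 4.8.1.
4. **SAP 4.8 and Table 5:** state the onset window for the general AE-rate summary and for the SAE and discontinuation row.
5. **Protocol:** reconcile 7.2 and 7.3 (AE and SAE reporting from first dose) with 3.6.3 and 4.1.2 (AEs recorded at all visits, including Visit 2). Without this the new table could rest on incomplete data, so a change to the SAP alone is not enough.

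The cost is a small protocol and eCRF clarification, one or two extra tables, and slightly less favourable AE counts. The design, randomization and efficacy analyses are unaffected.

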3.6.2 Efficacy Variables

- ADAS-Cog at Visits 3, 6, 9, 12, 13 and 14 or Early Termination

- MMSE at Visits 1, 3, 6, 9, 12, 13 and 14 or Early Termination
- CDR-Box at Visits 3, 6, 9, 12, 13 and 14 or Early Termination
- NPI at Visits 3, 6, 9, 12, 13 and 14 or Early Termination
- GDS at Visits 3, 6, 9, 12, 13 and 14 or Early Termination
- ADCS-ADL at Visits 3, 6, 9, 12, 13 and 14 or Early Termination
- Biomarkers in blood [Amyloid beta 40, Amyloid beta 42, Amyloid precursor protein intracellular domain (AICD), soluble neuregulin-1 (sNRG-1)] at Visits 3, 13 and 14 or Early Termination

The rating scales used in this study are ADAS-Cog (Alzheimer's Disease Assessment Scale-cognitive subscale), MMSE (Mini-mental status examination), CDR-SOB (Clinical Dementia Rating-Sum of Box), NPI (Neuropsychiatric Inventory), GDS (Geriatric Depression Scale) and ADCS-ADL (Alzheimer's Disease Cooperative Study Activities). All questionnaires that are subject-administered should be completed by the subjects alone or along with caregiver at the beginning of each visit to minimize influences from other procedures to be performed at that visit. A short explanation should be given to each subject about the purpose and the necessity of these questionnaires.

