3.6.3 Safety Variables

- Hematology, blood chemistry and urinalysis at Visits 1, 3, 6, 9, 12, 13 and 14 or Early Termination. See Section Appendix 1 for a complete list of laboratory tests to be done.
- ECG evaluation at Visits 1, 3, 6, 9, 12, 13 and 14 or Early Termination
- Complete physical examination at Visits 1, 3, 6, 9, 12, 13 and 14 or Early Termination
- Vital signs (sitting blood pressure, pulse, breathing, and temperature) and weight will be measured at all visits.
- MRI Scan of the brain at Visit 1, 9, 13 and 14 or Early Termination.
- C-SSRS at Visit 3, 6, 9, 12, 13, and 14 or Early Termination
- Data regarding AEs and concomitant medications will be collected at all visits

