4.4 Early Termination Visit

If a subject will drop-out the study before Visit 14 (Week 52), the clinical site will try to schedule an early termination visit. During this visit, the following assessments and procedures should be performed:

- The following questionnaires will be completed: ADAS-Cog (see Appendix 2), MMSE (see Appendix 3), CDR-SOB (see Appendix 4). NPI (see Appendix 5), GDS (see Appendix 6), ADCS-ADL (see Appendix 7) and C-SSRS (see Appendix 8).
- Measure vital signs (sitting blood pressure, pulse, breathing, and temperature) and weight.
- Perform a complete physical examination.
- Measure 12-lead ECG.
- Record any changes in concomitant medications.
- Record any adverse events, if applicable.
- Collect blood and urine samples for hematology, serum chemistry, pregnancy test (only for women of childbearing potential), biomarker analysis and urinalysis.
- Perform MRI scan including FLAIR and T2- weighted gradient-echo sequences.

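### The SAP 4.6.4 medication table counts ITT subjects but divides by the safety population, so percentages can be understated in an arm where a safety subject is outside ITT

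*SAP*

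**What the plan says.** SAP 4.6.4 (Prior and Concomitant Therapy) gives the counting population first: "Prior and concomitant medications will be tabulated for the ITT population by WHODDE ATC level 2 classifications, preferred term, and treatment". Later in the same paragraph it gives the denominator: "Percentages will be calculated using the total number of subjects in the safety population".

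SAP 4.3 defines the two sets by different data requirements. ITT takes "subjects who received at least one intravenous injection and have post-injection efficacy measurements". For the other set: "A safety population will include subjects who received at least one intravenous injection and have post-injection safety measurements". Both need one injection; they differ in the kind of follow-up data required.

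No other sentence in the SAP reconciles the two instructions.

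**The concern.** A percentage should count and divide over the same people. Here a subject can be in the denominator with no possibility of being counted. The table belongs to SAP 4.6, Treatment Group Comparability, so readers will compare the arms. With about 11 subjects per arm, one mismatched subject moves a row by several points.

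The omitted subject may also be an informative one. Protocol 3.3 requires withdrawal for use of a prohibited medication. If that happens before the first efficacy assessment and no efficacy score is obtained, the drug use is missing from the counts while the subject still enlarges the denominator.

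**Working it through.** **Can the two sets differ?**

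- Safety data: Protocol 3.6.3 says that vital signs "and weight will be measured at all visits". The first scheduled visit after the first injection visit is Visit 4, Week 2.
- Efficacy data: Protocol 3.6.2 lists "ADAS-Cog at Visits 3, 6, 9, 12, 13 and 14 or Early Termination". Visit 3 is baseline, so the first scheduled post-injection score is Visit 6, Week 6. The other scales follow the same post-baseline schedule.
- Early leavers: the Early Termination visit includes all the efficacy scales (Protocol 4.4), so a subject who attends it and is scored enters ITT. Protocol 3.3 says that a withdrawn subject must return for it, but Protocol 4.4 says only that "the clinical site will try to schedule an early termination visit".

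A subject who leaves between Weeks 2 and 6 and is not scored at an Early Termination visit is therefore in the safety population and not in ITT.

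**Inputs.** The documents state no medication percentage and no analysis-set counts, so there is no figure of the plan's own to reproduce. Assumptions: safety N in one arm S = 11 (SAP 3.2 plans about 11 per group); k = 0 to 3 safety subjects outside ITT; every ITT subject is also in the safety population. Then ITT N is I = S − k. Let x be the ITT subjects who took a drug and u the omitted subjects who took it (0 ≤ u ≤ k).

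**Formulas.**

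- Percentage as planned: x / S
- ITT count over ITT N: x / I, so planned / ITT = I / S
- Safety count over safety N: (x + u) / S, so the planned figure is short by u / S

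**Against an ITT base (S = 11).** The last two columns are for a row reported by every ITT subject, true ITT value 100%.

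| k | I / S | Planned value | Shortfall |
|---|---|---|---|
| 0 | 11/11 = 1.000 | 100% | 0 points |
| 1 | 10/11 = 0.909 | 90.9% | 9.1 points |
| 2 | 9/11 = 0.818 | 81.8% | 18.2 points |
| 3 | 8/11 = 0.727 | 72.7% | 27.3 points |

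Smaller rows move less: with k = 1 and x = 5, 5/11 = 45.5% is shown where 5/10 = 50.0% applies. In an overall column with S = 22 and k = 1 the factor is 21/22 = 0.955.

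**Against a safety base (S = 11, k = 1).**

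- x = 5, omitted subject did not take the drug: 5/11 = 45.5% both ways, no error.
- x = 5, omitted subject took it: 5/11 = 45.5% shown, 6/11 = 54.5% correct.
- x = 10, omitted subject took it: 10/11 = 90.9% shown, 11/11 = 100% correct. This could arise for AD medication, which inclusion criterion 5 requires of every subject, in any row that covers all the permitted drugs.
- x = 0, omitted subject took it: 0% shown, 1/11 = 9.1% correct. The drug is missing from the table.

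**Two side cases.** If a subject were in ITT but not in the safety population, the error would reverse (11/10 = 110%). The definitions allow this, but vital signs at every visit make it unlikely. Separately, the denominator sentence does not say that it is per arm. Read as both arms pooled, a treatment column could not exceed 11/22 = 50% even with identical sets.

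**The case against.** The strongest reply is that the sets may well coincide. An early leaver who attends the Early Termination visit and is scored is in ITT, so leaving before Week 6 is not enough by itself to create the mismatch. This stands and narrows the problem. It does not remove it, because Protocol 4.4 promises only an attempt at that visit.

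The second reply is that the harm is contained. SAP 4.1 shows counts beside percentages, SAP 4.6.1 reports the number in each analysis population, and SAP 4.6.4 lists medications by subject. No test uses the table, and SAP 4.2 plans no covariate adjustment. All of this stands, and it is why the point is minor.

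A reader might infer that every percentage is too low whenever a dosed subject is outside ITT. The documents do not support that. A dosed subject with neither kind of post-injection data is in neither set and changes nothing. Rows with no ITT user are unchanged relative to the ITT base, and with per-arm denominators the other arm is unaffected. If the safety population is the intended base, only drugs taken by the omitted subject are understated.

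A reader might also infer that the mismatch will create or hide an imbalance between arms. The documents give no analysis-set counts and no reason to expect early leavers to be more common in one arm, so this remains a possibility only.

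**Conclusion.** The inconsistency is real and can be seen within one paragraph of SAP 4.6.4. It has an effect only if a subject is in the safety population but not in ITT. In that arm, nonzero percentages are then below the ITT percentages by the factor ITT N / safety N: 0.909 with one such subject and 0.818 with two, on an assumed safety N of 11. Measured against the safety population, the shortfall is one subject in 11, or 9.1 points, for each omitted subject who took the drug, and zero for drugs that none of them took. If the sets coincide there is no error. The number of omitted subjects is assumed throughout. Only a descriptive table is affected; no efficacy or safety conclusion rests on it. The point is minor, but the text as written gives the programmer two populations for one percentage.

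**What to change.** In SAP 4.6.4, make two edits. Change the tabulated population from ITT to safety. Change the denominator to the number of subjects in the safety population in each treatment group. The first edit aligns count and denominator and keeps the medications of subjects who leave early; the second removes the pooled-arm reading. The safety population also fits Protocol 6.1.2, which summarises comparability variables for subjects valid for safety analysis, although that list does not name medications.

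The cost is a few words in one paragraph. It needs no new data and changes no test. The statistical section of the protocol specifies no medication table, so the protocol text does not have to change.
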